Appendix 2. Diagnostic Criteria for Atopic Dermatitis

Per Inclusion Criterion 2, a subject is to have a clinical diagnosis of atopic dermatitis according to the criteria of Hanifin and Rajka.⁴⁵

Table 8. Hanifin and Rajka's Diagnostic Criteria for Atopic Dermatitis

Major Criteria (must have at least three)

Pruritus

Typical morphology and distribution:

Adults: flexural lichenification or linearity

Children and infants: facial and extensor involvement

Chronic or chronically-relapsing dermatitis

Personal or family history of atopy (asthma, allergic rhinitis, atopic dermatitis)

Minor Criteria (must have at least three)

Xerosis

Ichthyosis/keratosis pilaris/palmar hyperlinearity

Immediate (type 1) skin test reactivity

Elevated serum IgE

Early age of onset

Tendency toward cutaneous infections (esp. staphylococcus aureus and herpes simplex), impaired cell-mediated immunity

Tendency toward non-specific hand or foot dermatitis

Nipple eczema

Cheilitis

Recurrent conjunctivitis

Dennie-Morgan infraorbital fold

Keratoconus

Anterior subcapsular cataracts

Orbital darkening

Facial pallor, facial erythema

Pityriasis alba

Anterior neck folds

Itch when sweating

Intolerance to wool and lipid solvents

Periofollicular accentuation

Food intolerance

Course influenced by environmental and emotional factors

White demographism, delayed blanch

1. VERSION HISTORY

This Statistical Analysis Plan (SAP) for study C3291002 is based on the protocol dated 06Jul2017.

Table 1. Summary of Major Changes in SAP Amendments

SAP Version	Change	Rationale
1	Not Applicable	Not Applicable
2	a. New TEAE definition was added 	a. Pfizer released new TEAE definition

2. INTRODUCTION

Crisaborole, also referred to as PF-06930164 and AN2728, is a low molecular weight benzoxaborole anti-inflammatory phosphodiesterase-4 (PDE-4) inhibitor that penetrates into the skin to the sites of inflammation. PDE-4 inhibition results in increased intracellular cyclic adenosine monophosphate (cAMP) levels. While the specific mechanism(s) by which crisaborole exerts its therapeutic action is not well defined, it is thought that crisaborole reduces the production of several inflammatory cytokines implicated in the pathophysiology of atopic dermatitis (AD).

Across the development program, crisaborole demonstrated an acceptable safety profile, with no crisaborole treatment-related serious adverse events (SAEs) (except 1 case of drug eruption in a Phase 2 study which was classified as possibly related), and the majority of adverse events (AEs) were mild and deemed unlikely or not related to investigational product. Safety and efficacy have not yet been established in patients younger than 2 years of age.

This 4-week study will evaluate the safety,  of crisaborole ointment 2%, applied twice daily (BID) in subjects who are 3 months to less than 24 months of age with mild-to-moderate AD. The dose selected for this study has been shown to be safe, well tolerated and efficacious in patients and healthy volunteers 2 years of age and older who participated in previously conducted studies. Based on these results and  satisfactory safety and local tolerability in the pediatric population to be enrolled in this study.

This SAP provides the detailed methodology for summary and statistical analyses of the data collected in study C3291002. This document may modify the plans outlined in the protocol; however, any major modifications of the primary endpoint definition or its analysis will also be reflected in a protocol amendment.

2.1. Study Objectives

2.1.1. Primary Objectives

- *To study the safety of crisaborole ointment 2% applied twice daily (BID) in children aged 3 months to less than 24 months with mild to moderate AD.*

[REDACTED]

■ [REDACTED]

■ [REDACTED]

2.2. Study Design

This is a Phase 4, multicenter, open label, safety study to evaluate the safety of crisaborole ointment 2% in children aged 3 months to less than 24 months with AD. CCI [REDACTED]

[REDACTED]

Approximately 125 subjects will be enrolled. Subjects will be between 3 months (at the time of the Screening visit) to less than 24 months of age at the time of Baseline/Day 1 with mild-to-moderate AD involving at least [REDACTED] assessed on Baseline/Day 1.

[REDACTED]

CCI

[REDACTED]

3. ENDPOINTS AND BASELINE VARIABLES: DEFINITIONS AND CONVENTIONS

3.1. Primary Endpoint(s)

- *Incidence of treatment emergent AEs (including application site reactions), SAEs, and clinically significant changes in height, weight, vital signs, ECG and clinical laboratory parameters.*

An adverse event is considered TEAE if the event start date is on or after the treatment period start date and prior to the treatment end date plus lag or within the Active Treatment Phase.

[REDACTED]

[REDACTED]

- [REDACTED]
- [REDACTED]
- [REDACTED]
- [REDACTED]
- [REDACTED]
- [REDACTED]

CCI [REDACTED]

- [REDACTED]
- [REDACTED]
- [REDACTED]

[REDACTED]

- [REDACTED]
- [REDACTED]
- [REDACTED]

3.3. Baseline Variables

Demographic and baseline characteristics include:

- Age (in months);
- Sex;
- Race;
- Ethnicity;
- Height (in cms);
- Weight (in kg);
- Body Mass Index;
- Duration of disease (in months);

For endpoints based on scheduled visits, baseline will be defined as the last evaluation taken before the time of the first dose of investigational product.

4. ANALYSIS SETS

4.1. Full Analysis Set

Any subject receiving ≥ 1 dose of investigational product will be included in full analysis set (FAS).

4.2. Per Protocol Analysis Set

None.

4.3. Safety Analysis Set

Any subject receiving ≥ 1 dose of investigational product will be included in safety analysis set.

CCI

4.5. Other Analysis Sets

N/A.

5. GENERAL METHODOLOGY AND CONVENTIONS

5.1. Hypotheses and Decision Rules

This is an open label safety study. There is no hypotheses and decision rules.

5.2. General Methods

In general, number and percent will be presented for categorical variables. Number, mean, standard deviation, minimum, 1st, 2nd and 3rd quartiles and maximum will be presented for continuous variables.

5.2.1. Analyses for Binary Data

Binary endpoints will be summarized using number, percentage and 95% CI of percentage.

5.2.2. Analyses for Continuous Efficacy Data

Continuous endpoints will be descriptively summarized using number, mean, standard deviation (standard error of the mean), minimum, 1st, 2nd and 3rd quartiles and maximum.

5.2.3. Analyses for Categorical Data

Categorical endpoints will be summarized using number and percentage.

5.3. Methods to Manage Missing Data

Missing values will not be imputed for safety, CCI

6. ANALYSES AND SUMMARIES

6.1. Primary Endpoint(s)

6.1.1. Adverse Events

Adverse events will be summarized according to Pfizer reporting standards for

- TEAEs;
- SAEs.

Overall TEAEs as well as treatment area TEAEs will be summarized by the number of subjects reporting any TEAE, system organ class (SOC), preferred term (PT), severity, relationship to investigational product, and seriousness.

Overall SAEs as well as treatment area SAEs will be summarized by SOC and PT, and individual SAEs will be listed by subject. A list of subjects who prematurely discontinued from the study due to an AE will be provided.

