| Dispense and weigh the investigational product tube(s) and apply first dose. First dose applied in office by study staff | | X | | | | | | |
| Dispense and weigh new investigational product tube(s) and provide for at-home dosing | | X ⁱ | X | X | | | | |
| At-home dosing, applied by parent(s)/legal guardian ^{i,j} | | 2nd dose (PM) on Day 1, then BID up to PM dose prior to Day 29 visit | | | | | | |
| Review dosing diary; assess compliance; re-train parent(s)/legal guardian if doses missed | | | X | X | X | X | | |
| Collect and weigh empty, partially used and unused investigational product tubes | | | X ⁱ | X | | X | | |
| Review and record prior and concomitant medications | X ^k | X | X | X | X | X | X | X |

| Day | | 1 | 8 | 15 | 22 | 29 | 36 | 57 |
|--|------------------|----------------|--------|---------|-------------------|------------------------------------|-------------------|---|
| Window | -28 to -2 day(s) | | ±1 day | ±3 days | ±3 days | ±3 days | ±3 days | +3 days |
| Visit | Screening | Baseline | | | Telephone Contact | End of Treatment/Early Termination | Telephone Contact | Follow-up Contact ^a (End of Study) |
| Assess for AEs (including application site reactions) and SAEs | X | X ¹ | X | X | X | X | X | X |
| Review lifestyle requirements | X | X | X | X | X | X | | |
| Schedule/reconfirm next study visit/contact | X | X | X | X | X | X | X | |
| Remind parent(s)/legal guardian to bring all investigational product tubes (empty, partially used and unused) and the dosing diary to the next visit | | X | X | X | X | | | |

Abbreviations: AD=atopic dermatitis; BP=blood pressure; [REDACTED] PR=pulse rate; RR=respiratory rate; AE=adverse event; SAE=serious adverse event; CCI [REDACTED]; BID=twice a day

- a. Follow-up contact will be completed 28 +3 calendar days after the last administration of the investigational product to capture any adverse events.
- b. Vital signs (temperature, respiratory rate, pulse rate, and BP) taken in seated or supine position after subject has been seated or lying face up for 5 minutes.
- c. A full physical examination will be performed at the Screening visit. If the full examination cannot be completed during screening, an unscheduled visit may be performed prior to Baseline/Day 1 to complete the full assessment.
- d. A limited physical examination will be performed at Baseline/Day 1.
- [REDACTED]
- [REDACTED]

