7.1.2. Physical Examination, including Height/Length, and Weight

Physical examinations, including height/length, and weight will be performed at times specified in the [STUDY PROCEDURES](#) section of this protocol.

Physical examinations may be conducted by a physician, trained physician's assistant, or nurse practitioner as acceptable according to local regulation. A full physical examination will include, but is not limited to the following organ or body systems: head, ears, eyes, nose, mouth, skin, heart and lung examinations, lymph nodes, gastrointestinal, musculoskeletal, abdomen (liver, spleen), cardiovascular, and neurological systems. In addition, an assessment will be made of the condition of all AD-involved skin.

The limited or abbreviated physical examination will be focused on general appearance, the respiratory, cardiovascular, and neurological systems, as well as towards symptoms reported by the subject's parent(s)/legal guardian. In addition, symptoms and signs of diarrhea and vomiting should be assessed to monitor for evidence of dehydration.

The neurological examination component of all physical examinations should include evaluation of clinical signs that have been associated, in published reports, with  toxicity²¹ including central nervous system depression, seizure activity, ataxia, as well as somnolence, poor feeding and irritability which are considered newly emergent and independent of the subject's AD related signs.

Results from blood pressure and prior ECG assessments should be referred to when performing the cardiovascular component of all physical examinations in order to actively monitor for clinical signs that have been associated, in published reports, with  toxicity including hypotension and cardiac arrhythmia.

For both weight and height/length measurements, the investigator or examiner should be trained in measuring height/length and weight as well as in calibration procedures. Ideally, the same person should measure the subject at every visit. Attempts should be made to schedule visits, so that measurements can be taken at approximately the same time throughout the study. The parent / caregiver is needed to help with measurement and to soothe and comfort the child. Explain to the parent/ caregiver the steps in the procedures and that it is important to keep the child still and calm to obtain good measurements.

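### No readable SAP table counts infants with at least one of the eight toxicity signs that protocol 7.1.2 tells examiners to look for; a pre-specified grouped row and a listing would supply it

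*SAP*

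**What the plan says.** Protocol 7.1.2 (Physical Examination) states: "The neurological examination component of all physical examinations should include evaluation of clinical signs that have been associated, in published reports, with" a substance whose name is redacted. It lists these signs as "including central nervous system depression, seizure activity, ataxia, as well as somnolence, poor feeding and irritability", and requires them to be new and separate from the infant's AD. The next paragraph does the same for the cardiovascular component, naming "toxicity including hypotension and cardiac arrhythmia". That makes eight signs, six neurological and two cardiovascular.

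Other data point the same way. The chemistry panel in protocol Table 2 includes lactate, osmolal gap and anion gap for all subjects. Protocol 6.8 times the Day 29 sample so that a redacted systemic level and lactate are drawn 12 ± 3 hours after the last evening application.

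In the SAP, section 6.1.1 reads "Overall TEAEs as well as treatment area TEAEs will be summarized by the number of subjects reporting any TEAE, system organ class (SOC") and continues with "preferred term (PT), severity, relationship to investigational product, and seriousness". For serious events it adds: "Overall SAEs as well as treatment area SAEs will be summarized by SOC and PT, and individual SAEs will be listed by subject". Subjects who discontinue because of an AE are also listed. Laboratory data, vital signs, ECG, growth and physical examination (SAP 6.1.2 to 6.1.6) each get a separate summary to sponsor standards. Other analysis sets (4.5) and subset analyses (6.3) are marked as not applicable.

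**The concern.** The protocol picks out a specific set of signs because together they would point to one toxicity in infants aged 3 to less than 24 months. The natural question is how many infants had any of them. The readable SAP plans no row that answers it. It does define a custom grouping for local events (treatment area) but gives the systemic signs no equivalent.

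Three things follow. First, several sparse preferred-term rows can each look like background although the number of affected infants is larger. Second, the rows cannot be added to recover that number, because one infant may appear in more than one. Third, the study is open-label and protocol 9.5 lets the sponsor review data while it runs, so a grouping made later would mean choosing terms after the events are known. With no hypothesis and a single arm (SAP 5.1), the descriptive tables are the study's answer to its primary safety objective.

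**Working it through.** **1. The plan's own figure.** Protocol 9.1 enrols 125 to obtain 100 completers with 20% dropout: 100 / (1 − 0.20) = 125. This reproduces. No alpha, power or event rate is stated, so the rest compares texts and adds an illustration.

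**2. Texts side by side.**

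| Protocol 7.1.2 asks for | Readable SAP output |
|---|---|
| Six neurological signs | TEAEs by SOC, PT, severity, relationship and seriousness (6.1.1); physical examination tables to sponsor standards (6.1.6) |
| Hypotension | The same TEAE tables; vital signs summarised separately (6.1.3) |
| Arrhythmia | The same TEAE tables; ECG summarised separately (6.1.4) |
| Infants with any of the eight | None found |
| Signs shown beside that infant's lactate and gaps | None found |

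**3. How the signs reach the database.** In the Schedule of Activities the full examination is at Screening and Day 29/early termination. The footnote for the remaining one reads "A limited physical examination will be performed at Baseline/Day 1". Once dosing has begun, the only scheduled examination in the readable schedule is therefore Day 29/early termination. A sign arising earlier would mostly be recorded as an AE, so the AE tables carry the weight.

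**4. What preferred-term rows can and cannot say.** Let k infants report each of the eight signs, with N = 125. The number with at least one sign lies between the largest single count and the sum of the counts:

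k ≤ number with any sign ≤ 8k.

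The values of k are assumptions; the documents give no rates.

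| k per sign | Lowest (complete overlap) | Highest (no overlap) |
|---|---|---|
| 1 (0.8%) | 1 / 125 = 0.8% | 8 / 125 = 6.4% |
| 2 (1.6%) | 2 / 125 = 1.6% | 16 / 125 = 12.8% |
| 3 (2.4%) | 3 / 125 = 2.4% | 24 / 125 = 19.2% |

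For k = 2 the exact (Clopper-Pearson) 95% CI is 0.2% to 5.7% at the low end and 7.5% to 20.0% at the high end. The same eight rows fit both.

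**5. Do SOC rows close the gap?** Only in part. A SOC row that counts subjects counts an infant once within that SOC, but it also contains every other term in the SOC. Suppose, favourably, that the six neurological signs made up one SOC row and the two cardiovascular signs another, with nothing else in either. Rows of 12 and 4 would still leave the combined count anywhere from 12 (all overlap) to 12 + 4 = 16.

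**6. What a linked listing could show.** Scheduled chemistry, including lactate and the gaps, is at Screening and Day 29, plus a pre-dose Day 8 sample in the PK cohort. After baseline, vital signs are taken at Days 8, 15 and 29, and ECG at Days 8 and 29. An event in the second week of dosing would, for most infants, be matched to a Day 29 laboratory value unless an unscheduled sample was drawn.

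**The case against.** The strongest objection is that absence cannot be proved from a redacted document. The toxicity is blacked out, as are the SAP text between 6.1.6 and 6.3, the SAP endpoints after 3.1, and parts of protocol section 9. The timed Day 29 sample makes it plausible that a redacted analysis of this substance exists, and the sponsor's reporting standards were not supplied. This stands as a limit on the claim. SAP 6.1.1, where a grouped AE row would be expected, shows no redaction.

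Second, protocol 7.1.2 tells examiners what to look for and promises no grouped analysis. That is true: this is a gap in usefulness and not a contradiction between the documents.

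Third, there are other routes to the information. SAEs and AE discontinuations are listed by subject. Protocol 8.2.3 gives convulsions without hospitalisation as an example of an important medical event, so a seizure would probably appear in the SAE listing. An external DMC monitors safety under a charter not provided, and the count can be derived from subject-level data at any time. All of this stands. What remains uncovered is the non-serious event that does not lead to discontinuation, such as somnolence or poor feeding, and the guarantee that the terms were chosen in advance.

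Fourth, a pooled percentage that mixes irritability with seizures has no comparator. That also stands, and is why the non-specific terms should be shown separately as well.

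**Conclusion.** The point holds as a cheap improvement. The protocol defines a set of eight signs, and no readable SAP table counts infants with at least one of them. The size is an uncertainty in what would be reported: under an assumed 2 of 125 infants per sign, the combined figure could be 1.6% to 12.8%, and the planned rows do not settle it.

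Some stronger readings are tempting, and the documents do not support them:

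- A reader might infer that AEs are reported only by SOC and PT. They are also summarised by severity, relationship and seriousness, with a treatment-area split and some listings; none of these groups the named signs.
- A reader might infer that a combined signal cannot be seen, or that the trial cannot answer its safety question. The supported statement is that no readable planned table shows it.
- A reader might take about 12% as the size, from 1 − (1 − 0.016)^8 = 12.1%. That assumes independent signs. Signs of one toxicity would tend to cluster within infants, and 12.1% is close to the 12.8% maximum. The range is the honest statement.
- A reader might infer scatter over several SOCs. The documents give no SOC for any sign and support only the neurological/cardiovascular split.

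The conclusion assumes that the redacted text and the sponsor's standards contain no equivalent table.

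**What to change.** If a grouped summary already exists in a redacted section or in the sponsor's standards, cross-reference it from SAP 6.1.1. Otherwise add to 6.1.1:

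- A preferred-term list for the signs in protocol 7.1.2, fixed before data review.
- One summary of infants with at least one TEAE on the list: number, percentage and exact 95% CI, overall and treatment-related. SAP 5.2.1 already calls for a 95% CI on binary endpoints.
- The non-specific terms (irritability, poor feeding, somnolence) also shown separately.
- A subject listing with onset day and the nearest available lactate, osmolal gap, anion gap, systemic level, blood pressure and ECG, each with its date. A note should say that scheduled chemistry is at Screening and Day 29, plus Day 8 in the PK cohort.

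The cost is one SAP paragraph, one table and one listing from data already planned, with no change to sample size or conduct. The downsides are that ordinary infant complaints will enter the group, there is no comparator, and laboratory values will often not coincide with onset.

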6.1.2. Laboratory Data

Clinical laboratory values and change from screening at Day 29/Early Termination and clinical significant change will be summarized according to Pfizer standards.

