SCHEDULE OF ACTIVITIES

The schedule of activities table provides an overview of the protocol visits and procedures. Refer to the [STUDY PROCEDURES](#) and [ASSESSMENTS](#) sections of the protocol for detailed information on each procedure and assessment required for compliance with the protocol.

The investigator may schedule visits (unplanned visits) in addition to those listed in the schedule of activities table, in order to conduct evaluations or assessments required to protect the well-being of the subject.

All Subjects (Including non-PK and CC Cohorts)

| Day | | 1 | 8 | 15 | 22 | 29 | 36 | 57 |
|--|--|--|--|--|-------------------|--|-------------------|---|
| Window | -28 to -2 day(s) | | ±1 day | ±3 days | ±3 days | ±3 days | ±3 days | +3 days |
| Visit | Screening | Baseline | | | Telephone Contact | End of Treatment/Early Termination | Telephone Contact | Follow-up Contact ^a (End of Study) |
| Informed Consent | X | | | | | | | |
| Demographics | X | | | | | | | |
| Review Inclusion/Exclusion Criteria | X | X | | | | | | |
| Medical History | X | X | | | | | | |
| Confirmation of Diagnosis of AD | X | X | | | | | | |
| Height/Length and Weight | X | X | | | | X | | |
| Vital Signs ^b | X | X | X | X | | X | | |
| Full Physical Examination | X ^c | | | | | X | | |
| 12-Lead Electrocardiogram (ECG) | X | or X | X | | | X | | |
| Limited Physical Examination | | X ^d | | | | | | |
| [REDACTED] | [REDACTED] | [REDACTED] | [REDACTED] | [REDACTED] | | [REDACTED] | | |
| Body Site checklist of AD lesions | | X | X | X | | | | |
| [REDACTED] | | [REDACTED] | [REDACTED] | [REDACTED] | | [REDACTED] | | |
| [REDACTED] | [REDACTED] | [REDACTED] | | | | | | |

| Day | | 1 | 8 | 15 | 22 | 29 | 36 | 57 |
|---|---|--|----------------|---------|-------------------|---|-------------------|---|
| Window | -28 to -2 day(s) | | ±1 day | ±3 days | ±3 days | ±3 days | ±3 days | +3 days |
| Visit | Screening | Baseline | | | Telephone Contact | End of Treatment/Early Termination | Telephone Contact | Follow-up Contact ^a (End of Study) |
| Blood collection for serum chemistry and hematology | X ^g | | | | | X | | |
|  |  | | | | |  | | |
| Record treatable AD areas (excluding scalp) in source and provide parent(s)/legal guardian with documentation of the designated treatment areas | | X | | | | | | |
| Dispense dosing diary and instruct the subject's parent(s)/legal guardian on use | | X | X | X | | | | |

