- g. Blood draw for clinical labs may be completed any time during the screening period, (Day -28 to Day -2) however the results must be available and reviewed by the PI prior to the Baseline/Day 1 visit and investigational product application. If the laboratory sample cannot be obtained due to an upset child, parent or other collections issues, the subject will not be enrolled into the study. Serum chemistry laboratory assessments include lactate and parameters needed to perform calculation of osmolal gap and anion gap.
- [REDACTED] CCI [REDACTED]
- i. Not applicable to subjects in C [REDACTED] cohort through Day 8.
- j. In the event the scheduled Day 29 visit does not fall exactly on Day 29, instruct parent(s)/legal guardian to keep dosing BID until the evening dose prior to the Day 29 visit.
- k. All medications and non-medication therapies used within 30 days prior to Screening.
- l. Assess for AEs (including application site reactions) /SAEs before and after in clinic dose at Baseline/Day 1.

CC Cohort Subjects Only

| Day | 1 ^a | 2-7 | 8 ^b Prior to AM dose (168 hours ±1 hour post time of AM application on Day 1) | 8 3 hours ±20 minutes after completion of AM dose | 8 12 hours ±1 hour after completion of AM dose | Non-PK Study Schedule (see above) ^c |
|---|----------------|-----|---|--|---|--|
| Visit | CCI | | | | | |
| CCI | | | | | | |
| CCI | | | | | | |
| Blood collection for serum chemistry ^{d,f} | | | X | | | |
| CCI | | | | | | |
| Review lifestyle requirements | X | X | X | | | |
| Assess and record any pre- and/or post-dose AEs (including application site reactions) and SAEs | X | X | X | | | |
| Assess and record any changes in concomitant medications | X | X | X | | | |
| Weigh amount of investigational product to be applied before each dose application | X | X | X ^h | | | |
| Dispense dosing diary and train parent(s)/legal guardian on use | | | X | | | |
| Dispense and weigh investigational product tube(s) and provide for at-home dosing | | | X | | | |
| Review the schedule of upcoming study visits with the parent(s)/legal guardian | X | X | X | | | |
| Remind parent(s)/legal guardian to bring all investigational product tubes and the dosing diary to the next visit | | | X | | | |

Abbreviations: CCI

- Perform Day 1 assessments prior to dosing procedures, as applicable (See All Subjects (Including non-C and C Cohorts)).

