- Aside from AM dose application, first C sample collection, serum chemistry CCI sample collection which must all be performed at the first C collection time point, all other Day 8 procedures may be performed at any of the 3 PK collection time points.
- Subject to resume regular study schedule following completion of Day 8/PK 8 final PK sample collection.

█ CCI [Redacted]

█ CCI [Redacted]

f. Serum chemistry laboratory assessments include lactate and parameters needed to perform calculation of osmolal gap and anion gap.

█ CCI [Redacted]

h. Weighing of investigational product on Day 8 applies to the AM dose only.

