1.4. Rationale

1.4.1. Study and Dose Rationale

This 4-week safety study will evaluate the safety profile of crisaborole ointment 2% BID in subjects who are 3 months to less than 24 months of age with mild-to-moderate AD. In addition, [REDACTED] will be assessed in a subgroup of at least 16 subjects under maximal use conditions, defined as systemic exposure conditions related to a high percent of body surface area involvement which would maximize the potential for drug absorption with anticipated clinical use of crisaborole. While crisaborole has been studied extensively in patients and healthy volunteers 24 months of age and older, it has not been tested in patients less than 2 years of age. As such, the current study is being conducted as a post-approval commitment to FDA as part of the pediatric study plan.

The dose strength and regimen selected for this study has been shown to be safe, well tolerated and efficacious in patients and healthy volunteers 2 years of age and older who participated in previously conducted studies of crisaborole. Crisaborole ointment 2% applied BID was studied in two Phase 3, randomized, double-blind, vehicle-controlled studies, and a Phase 3 open-label long-term safety study. Data from the two controlled studies showed a statistically significant therapeutic effect compared to vehicle with no safety concerns in patients 2 years and older. In the open-label study, crisaborole ointment 2% applied BID,

demonstrated that the long-term use was well tolerated and not associated with any systemic safety signals. The Phase 1 maximal use absorption study in children and adolescents aged 2 to 17 years old,³⁶ showed that subjects who were administered crisaborole ointment 2% BID (single dose on Days 1 and 8) to [REDACTED] had overall blood levels of crisaborole that were similar to those previously observed in adults after [REDACTED]. An analysis of variance (ANOVA) showed no statistically significant differences in CC parameters between the age cohorts represented in the study (Cohort 1, ages 12–17 years; Cohort 2, ages 6–11 years; and Cohort 3, ages 2–5 years).

Based on the results of clinical studies conducted with crisaborole ointment 2% to date, it is anticipated that crisaborole ointment 2% will demonstrate similar efficacy and satisfactory safety and local tolerability in the pediatric population to be enrolled in this study.

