6.1.3. Vital Signs

Vital signs and change from baseline and clinical significant change will be summarized according to Pfizer standards.

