6.1.4. ECG

ECG and change from baseline and clinical significant change will be summarized according to Pfizer standards.

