6.1.5. Height/Length and Weight

Height/length and weight values and change from baseline at Day 29/Early Termination and clinical significant change will be summarized according to Pfizer standards.

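### Does naming laboratory change only at Day 29/Early Termination leave the maximal-use cohort's Day 8 chemistry unanalysed?

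*SAP*

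**What the plan says.** SAP 6.1.2 (Laboratory Data) reads: "Clinical laboratory values and change from screening at Day 29/Early Termination and clinical significant change will be summarized according to Pfizer standards".

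The neighbouring sections follow two patterns:

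- Vital signs (SAP 6.1.3) and ECG (SAP 6.1.4) carry no visit limit: "Vital signs and change from baseline and clinical significant change will be summarized according to Pfizer standards" and "ECG and change from baseline and clinical significant change will be summarized according to Pfizer standards".
- Height/length and weight (SAP 6.1.5) carry the single-visit wording: "Height/length and weight values and change from baseline at Day 29/Early Termination and clinical significant change will be summarized according to Pfizer standards".

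In the Protocol's Schedule of Activities, the table for all subjects has a row for "Blood collection for serum chemistry and hematology", marked at Screening and at Day 29/Early Termination only. The separate cohort table has a row for "Blood collection for serum chemistry", marked once, on Day 8 before the morning dose. Its footnote adds: "Serum chemistry laboratory assessments include lactate and parameters needed to perform calculation of osmolal gap and anion gap". Protocol 1.4.1 describes this cohort as a "subgroup of at least 16 subjects under maximal use conditions".

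SAP 3.1 defines the primary endpoint as the incidence of treatment-emergent adverse events, serious adverse events and clinically significant changes in several safety measures, laboratory parameters among them. Mean laboratory change is not part of it.

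**The concern.** The laboratory section seems to have been written from the all-subjects schedule. Measures taken at several on-treatment visits get open wording, and height and weight, taken once on treatment, get the Day 29 wording. Laboratory data get the Day 29 wording too, although the cohort has two scheduled draws after first dose.

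The omitted visit is an informative one. The cohort exists to maximise absorption. Up to Day 8 its doses are applied at the site or by a visiting professional and are weighed (Protocol 5.2 and 5.10); after that, weighing each dose is no longer required. Day 8 is therefore the chemistry most closely tied to known exposure.

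Protocol 7.1.1 reserves clinical significance for abnormal values with clinical manifestations or a need for intervention. If the SAP count follows that definition, a group shift in lactate or in either gap that stayed below it could go unreported as a change.

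**Working it through.** **Scheduled visits after first dose against the SAP wording**

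| Measure | Scheduled visits after first dose | Visit named in the SAP for change |
|---|---|---|
| Vital signs | Days 8, 15, 29 (3) | none, so open |
| ECG | Days 8, 29 (2) | none, so open |
| Height/length, weight | Day 29 (1) | Day 29/Early Termination |
| Chemistry, non-cohort subjects | Day 29 (1) | Day 29/Early Termination |
| Chemistry, maximal-use cohort | Days 8, 29 (2) | Day 29/Early Termination |

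One of the cohort's two draws therefore has no named change summary.

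**Who is affected.** Protocol 9.1 plans 125 subjects, from 100 completers and 20% dropout: 100 / (1 − 0.20) = 125, which reproduces. At the planned minimum the cohort is 16 / 125 = 12.8%, leaving 125 − 16 = 109 subjects for whom the wording is exact.

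**What each part of the SAP 6.1.2 sentence covers**

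1. *Laboratory values.* The Day 29 phrase follows the words on change from screening and can attach to change alone. Values at all laboratory visits, Day 8 included, then fall within the sentence.
2. *Change from screening.* Named for Day 29/Early Termination only. This is the gap.
3. *Clinically significant change.* No visit limit here or in Protocol section 9. This is the primary-endpoint component, and Day 8 is inside it.

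A reader with Day 8 values and screening values in the same output has the ingredients of the change. Under Protocol 8.2.2 an abnormal result also becomes an adverse event if it has symptoms, prompts further testing or intervention, alters dosing, or is considered an adverse event by the investigator or sponsor.

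**What a Day 8 change table could add.** The documents give no SD for lactate or the gaps, so results are in SDs of change. Sizes of 12 and 20 are assumed, to show the range around 16.

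- Half-width of the 95% CI for a mean change = t(0.975, n − 1) / √n. For n = 16: 2.131 / 4 = 0.53 SD. For n = 12: 0.64. For n = 20: 0.47.
- A half-width is not a detectable shift. From the noncentral t distribution with n = 16, a true shift of 0.53 SD gives an interval excluding zero about 51% of the time. To reach 80% the shift must be about 0.75 SD (0.89 with 12, 0.66 with 20).
- For comparison, if no cohort infant has a clinically significant change, the exact two-sided 95% upper bound on the rate is 1 − 0.025^(1/n): 20.6% for 16, 26.5% for 12, 16.8% for 20.

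SAP 5.2 and 5.2.2 list no confidence interval for continuous data, so a table built to the SAP's conventions would show means, SDs and quartiles without even this interval.

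**The case for a change.** The best case for a change is that it costs almost nothing. The blood is already drawn from infants by scheduled venepuncture, and naming Day 8 in SAP 6.1.2 would settle any doubt about what the sentence covers. There is also a missing-data argument. Protocol 6.12 does not treat omitted early-termination procedures as deviations so long as safety was preserved, and SAP 5.3 imputes no safety values. An infant who left after Day 8 without final bloods would then have Day 8 as the only scheduled on-treatment chemistry, and it would enter no named change summary.

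That scenario is real but small. If the 20% overall dropout applied to the cohort (an assumption), it would involve at most 0.20 × 16 = 3.2 infants, fewer once those leaving before Day 8 or giving final bloods are set aside. Their Day 8 values and any clinically significant change would still be within the other two parts of the sentence.

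The argument from the SAP's wording pattern also stands as far as it goes: the sentence probably was drafted from the all-subjects table. It does not show that the cohort's results were to be dropped. Nor does the entry of not applicable under SAP 6.3 (Subset Analyses), since SAP 6.4.1 reports a blacked-out item alongside the overall safety analysis set. Cohort-specific text is blacked out in or after SAP 2.2, 3.1, 4.3 and 6.1.6, and one footnote to the Day 8 chemistry row is not visible. A Day 8 summary could lie in any of these, and redacted text cannot be counted as absent.

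The point about sub-threshold shifts is weaker than it looks. The SAP refers clinically significant change to sponsor standards that are not reproduced, so it is not established that the Protocol 7.1.1 definition governs the count.

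**Conclusion.** The reading of the visible text is right: SAP 6.1.2 names change from screening at Day 29/Early Termination and names none for the cohort's Day 8 chemistry. No change to the plan is needed. Followed as written, it delivers the laboratory component of its primary endpoint at every visit, Day 8 included, and the same infants have chemistry again at Day 29. The gap is one descriptive change column, for one visit, in about 16 of 125 subjects, in a study without hypotheses or a control arm. An analyst producing standard output by visit would fill it without instruction. Naming Day 8 would be harmless tidying, but it would not alter any conclusion the study is designed to reach.

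This rests on two assumptions: that laboratory values are tabulated at each scheduled visit, which the sentence permits but does not state, and that clinically significant change is counted over all visits after baseline, since no limit is given. Whether the blacked-out text already holds a Day 8 change summary cannot be determined from the public documents.
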